4.7.4 Pharmacokinetic Inferential Statistics

The dose proportionality of the key nanatinostat PK parameters C_{max} , $AUC_{0-\infty}$ and AUC_{0-6h} , if appropriate over the administered dose range, will be assessed using the following model using all dose groups:

$$\log(\text{parameter}) = a + b * \log(\text{dose})$$

where 'a' is the intercept and 'b' is the slope. The model will be fit to the pooled, individual group patient data. Parameter estimates of b, including the standard error and 90% CIs will be summarized in a table. If the 90% CI for b includes 1.0, then linearity will be concluded.

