3.3. Tablet Cohort

Once the Phase 2 arm has completed enrollment, approximately 10 patients will be enrolled into a cohort to receive VRx-3996 tablets instead of capsules. Approximately 10 patients will be needed to provide an assessment of systemic exposures to VRx-3996. The dose and schedule of VRx-3996 and valganciclovir administered to patients in the tablet cohort will be the RP2D

(VRx-3996 20 mg PO QD for 4 days on and 3 days off in a 7-day regimen with valganciclovir 900 mg PO QD starting at C1D1). VRx-3996 and valganciclovir will be taken at the same time for all visits.

The intent of these evaluations will be important to the clinical development program for assessing comparability of exposures to VRx-3996 administered as a tablet presentation, for comparison to delivery of the oral capsule product. The tablet form of VRx-3996 allows for a reduction from four 5 mg capsules to two 10 mg VRx-3996 tablets per dose on a daily basis and is expected to be less of a burden for patients.

With exceptions as described in the protocol, patients will follow the protocol/assessments as detailed for the Phase 2 expansion cohort patients.

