12.4. Analysis of the Secondary Endpoints

12.4.1. Pharmacokinetics (PK)

For all cohorts in Phase 1b and the Tablet cohort of Phase 2, the PK of VRx-3996 and valganciclovir will be summarized by descriptive statistics. For valganciclovir, PK analysis will be conducted on ganciclovir. Pharmacokinetic parameters will be estimated, where appropriate, by non-compartmental analysis using statistical computer packages as specified in the Statistical Analysis Plan. Graphic evaluation will be used for data analysis where appropriate. Pharmacokinetics and fit will be evaluated graphically, and by modeling if sufficient data are available.

Serial blood samples for PK analysis will be collected from all subjects at pre-specified timepoints. The following PK parameters of VRx-3996 and ganciclovir may be calculated but are not limited to:

- Area under the concentration-time curve from administration to time t (AUC_{0-t})
- Area under the concentration-time curve from administration to infinity ($AUC_{0-\infty}$)
- Maximum concentration (C_{max})
- Time to maximum concentration (T_{max})
- terminal elimination half-life ($t_{1/2}$)
- Apparent volume of distribution (V_z/F)
- Apparent clearance (CL/F)

Individual elapsed sampling times will be used in the pharmacokinetic analysis. C_{max} and T_{max} will be obtained directly from the experimental observations. AUC_{0-t} will be calculated using the linear trapezoidal rule.

$AUC_{0-\infty}$ will be calculated according to the following equation:

$$AUC_{0-\infty} = AUC_{0-t} + \left(\frac{C_{last}}{\lambda_z} \right)$$

where the C_{last} is the last quantifiable concentration.

For the purpose of calculating AUC_{0-t} , when two consecutive plasma concentrations below the lower limit of quantification (LLOQ) are encountered after T_{max} , all subsequent values will be excluded from the analysis. When embedded missing values occur, they will be excluded from the analysis. Any quantifiable concentrations at pre-dose will be set to zero.

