4.2 Analysis Sets

The analysis sets are defined as follows:

- Intent-to-Treat (ITT) Set: The ITT includes all enrolled patients.
- Safety Analysis Set: includes all enrolled patients who receive at least one dose of nanatinostat.
- Efficacy Evaluable Set: includes all patients with measurable/evaluable disease at screening who have met all eligibility criteria and have at least one evaluable post-baseline efficacy tumor assessment.
- Pharmacokinetic Analysis Set: includes all patients in the ITT who have received at least one post-dose PK sample obtained and analyzed (i.e. valid result being

available). The PK Analysis Set is used for tabulation of nanatinostat and ganciclovir concentrations from PK plasma samples.

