4.7 Pharmacokinetics

The PK Analysis Set will be used for individual plasma concentration listings and summaries of plasma concentrations. The PK Population will also be used for individual and mean figures for plasma concentrations.

The PK Analysis Set will be used for noncompartmental analyses (NCA), inferential statistics, PK parameter listings, and parameter summaries.

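### The dose-proportionality slope in SAP 4.7.4 is partly confounded with formulation, because tablet patients enter the pooled model only at the top dose and the model has no formulation term; the effect is modest and cheap to remove.

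*SAP*

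**What the plan says.** SAP 4.7.4 says that dose proportionality for Cmax, AUC0-∞ and AUC0-6h of nanatinostat "will be assessed using the following model using all dose groups". The model is log(parameter) = a + b·log(dose), "where 'a' is the intercept and 'b' is the slope". No other term is in the model. On the data used, the section says: "The model will be fit to the pooled, individual group patient data". The decision rule is: "If the 90% CI for b includes 1.0, then linearity will be concluded".

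Who enters follows from two other sections. SAP 4.7 states: "The PK Analysis Set will be used for noncompartmental analyses (NCA), inferential statistics, PK parameter listings, and parameter summaries". SAP 4.2 defines that set without regard to formulation: it "includes all patients in the ITT who have received at least one" post-dose PK sample with a valid result. SAP 4.7.2 has serial samples on Cycle 1 Day 1 from every patient. Phase 1b, Phase 2 capsule and tablet patients are therefore all in.

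The tablet is studied at the RP2D only (protocol 2.2), which is 20 mg per dose (protocol 3.3). Protocol Table 5 has capsule cohorts taking 5 mg (cohort 2a), 10 mg (1, 2b, 2c) and 20 mg (3) per administration. Protocol 3.3 gives the tablet cohort's purpose as "assessing comparability of exposures to VRx-3996 administered as a tablet presentation" against the capsule.

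**The concern.** Tablets appear at one dose level and that level is the top one, so formulation and dose are correlated in the data. With formulation left out of the model, least squares assigns part of a tablet/capsule difference to the dose slope. Pooling takes equal exposure from the two forms as given, although the tablet cohort was added to examine exactly that. The comparability evidence cited in protocol 5.1.2 and SAP 3.3.1.1 is in vitro dissolution and dog pharmacokinetics, not human data.

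The error can go either way. Higher tablet exposure raises b, and lower tablet exposure reduces it. A true departure among capsules can be pulled towards 1.0, and a proportional capsule can be pushed away from it. What is at stake is the meaning of b and the linearity statement attached to it.

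**Working it through.** The documents give no sample size, expected slope or precision for this model, so there is no planned figure to reproduce. The check is the omitted-variable formula for a straight-line fit.

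**Inputs**
- Phase 1b about 25 patients (SAP 3.1.1); Phase 2 capsule 30 (SAP 4.8); tablet about 10 (protocol 3.3).
- Cohort 1 has 7 patients, 4 + 3 (SAP 4.9). The other 18 Phase 1b patients are split by assumption: 2a 4, 2b 4, 2c 4, cohort 3 6.
- By dose per administration: 5 mg n = 4; 10 mg n = 7 + 4 + 4 = 15; 20 mg capsule n = 6 + 30 = 36; 20 mg tablet n = 10; total 65.
- Between-patient CV of 74% (AUC0-∞) and 100% (Cmax): the 40 mg column of protocol Table 4, from the earlier single-agent study. Log-scale SD s = √ln(1 + CV²) = 0.66 and 0.83.
- Tablet/capsule exposure ratio R: no value is given in the documents, so a range is used.

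**Formulas**
- Let x = ln(dose). Expected slope = true capsule slope + w·ln R, where w = Σ over tablets of (x − x̄) ÷ Sxx.
- SE(b) = s ÷ √Sxx.

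**Share passing into b, all patients.** Count dose in doublings (5 mg = 0, 10 mg = 1, 20 mg = 2).
- Mean = (15 + 92)/65 = 1.646.
- Sum of squares about the mean = 199 − 107²/65 = 22.86, so Sxx = 22.86 × (ln 2)² = 10.98.
- w = 10 × (2 − 1.646) ÷ (22.86 × 0.693) = 0.22.

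**Shift in b**
- R = 1.25: 0.223 × 0.223 = +0.05.
- R = 1.5: 0.223 × 0.405 = +0.09.
- R = 2: 0.223 × 0.693 = +0.15.
- Ratios of 0.80 and 0.5 give −0.05 and −0.15.

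**Precision, all patients.** 1/√10.98 = 0.302, so SE(b) = 0.66 × 0.302 = 0.20 at CV 74% and 0.83 × 0.302 = 0.25 at CV 100%.

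**Effect on the decision rule.** Simulation with true b = 1 and CVs from 57% to 138% (20,000 trials per setting) gave these probabilities that the 90% interval excludes 1.0:
- no formulation difference: about 10%, as it should be;
- R = 0.80 or 1.25: 10% to 12%;
- R = 0.5 or 2: 13% to 20%.

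**Masking.** With a true capsule slope of 1.3 and R = 0.5, the expected slope is 1.3 − 0.15 = 1.15.

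**Capsules only, or a formulation term.** The 55 capsule patients give 159 − 87²/55 = 21.38, Sxx = 10.27 and 1/√Sxx = 0.312. The SE is 0.312/0.302 = 1.03 times the pooled one. A formulation term gives the same slope, because tablets at a single dose fix only their own level.

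**Sensitivity**
- Another Phase 1b split (2a 3, 2b 3, 2c 5, cohort 3 7) gives w = 0.23.
- Reading dose as total daily dose gives w = 0.27; SAP 4.7.4 does not say which is meant.
- Phase 1b plus tablet only (20 mg capsule n = 6): w = 0.60, shifts of +0.13 at R = 1.25 and +0.24 at R = 1.5, and SE 0.24 to 0.30. Dropping tablets there raises the SE factor from 0.362 to 0.460, or 27%.

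**The case against.** Four points can be made for the plan.

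First, a reader might infer that any tablet/capsule difference will be declared non-proportionality. The documents do not support that. SAP 4.7.4 departs from linearity only when the 90% interval excludes 1.0, and at ratios of 0.80 or 1.25 that happens about as often as with no formulation difference at all.

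Second, a reader might take the larger shifts from protocol 12.4.1, which plans PK summaries "For all cohorts in Phase 1b and the Tablet cohort of Phase 2" and does not name the Phase 2 capsule patients. That sentence concerns descriptive summaries. The SAP's own set for inferential PK includes the Phase 2 capsule patients, so the 60% pass-through is a sensitivity case and not the plan.

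Third, it is tempting to say that tablet data add almost no precision. That is fair with Phase 2 capsules in the model (3%), but not without them (27%). In the smaller data set pooling can even be the more accurate choice. At R = 1.25 and CV 74%, root-mean-square error is √(0.239² + 0.133²) = 0.274 pooled against 0.304 for capsules only, and pooling stays ahead up to a ratio of about 1.37 (1.49 at CV 100%). With all patients, total error at R = 1.25 is about equal: 0.206 either way at CV 74%, and 0.256 against 0.260 at CV 100%.

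Fourth, the SAP already reports by cohort and phase, with a capsule column in tables (4.1.1), and summarises PK parameters by treatment (4.7.3). Tablets would not be hidden. The study is described as exploratory, the RP2D is already set, and SAP 4.7.4 carries an if-appropriate qualifier.

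All four stand as limits on size. None removes the confounding: the separate summaries do not reach the 4.7.4 model, and the qualifier names no formulation criterion.

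**Conclusion.** The point holds as a minor one. As written, b mixes dose with formulation, and under the assumed sizes about 22% of the log exposure ratio enters it. For ratios of 1.25 to 1.5 that is roughly a fifth to under half of one standard error, and the linearity conclusion would usually be unchanged. The direction is not known in advance, so the mixing can mask a departure as well as create one.

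This rests on the assumed Phase 1b split (only cohort 1 is documented), on CVs from 40 mg in an earlier study, on dose per administration, and on hypothetical ratios. Nothing in the documents shows that the tablet and capsule differ in patients. A tablet patient could be below 20 mg by Cycle 2 after a dose reduction, but AUC0-∞ is a Cycle 1 Day 1 parameter; the SAP does not say which visit supplies Cmax and AUC0-6h to this model.

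**What to change.** In SAP 4.7.4, replace the all-dose-groups wording with one of two statements: the model is fitted to all capsule patients from Phase 1b and Phase 2, or it includes a capsule/tablet term. The slope is the same in both; the second also gives an estimate of the tablet/capsule ratio, which serves the cohort's purpose. In the same sentence, name the cohorts that enter, and say whether dose is per administration or daily and which visit is used.

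The cost is one phrase in the SAP, no new data, and a standard error of b about 3% larger. If Phase 2 capsule data turned out to be unavailable, the increase would be about 27%. Pooling could then have lower total error for small formulation differences, and the pooled fit could be kept as a labelled sensitivity analysis.

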Exposure to VRx-3996 (area under the curve [AUC]) was broadly proportional over the dose range tested. At 40 mg daily, plasma concentrations exceeded 10 ng/mL for approximately 8 hours, a concentration associated with antitumor efficacy in preclinical models. There was no apparent accumulation between Day 1 and 28. The use of proton pump inhibitors did not appear to reduce absorption.

Table 4: PK Parameters of VRx-3996

Dose (mg/day)	5	10	20	40	80	120	160
Number of patients	3	4	3	10	10	4	5
Mean C_{max} ng/mL (CV%)	18 (121)	34 (91)	54 (68)	259 (100)	359 (167)	340 (114)	774 (74)
Median T_{max} h (range)	4 (2–4)	1 (0.3–4)	4 (0.3–4)	1 (0.3–4)	1 (0.3–4)	1 (1–2)	1 (0.3–4)
Mean $AUC_{0-\infty}$ ng·h/mL (CV)	*	111 (57)	93 [#]	630 (74)	1214 (138)	888 (103)	1985 (66)

Abbreviations: $AUC_{0-\infty}$ = area under the concentration-time curve from administration to infinity; C_{max} = maximum concentration; T_{max} = time to maximum concentration.

* No reliable estimate of terminal elimination rate constant for this cohort.

[#] Only one reliable observation.

The pharmacodynamic effect of VRx-3996 was evaluated by acetylation of histone H3 in peripheral blood mononuclear cells (PBMCs). Samples were collected on Days 1 and 28 of the first course of therapy, and values normalized to pretreatment levels. Increased histone acetylation was apparent 4 hours after drug administration and returned towards baseline by 24 hours. Increases in histone acetylation were first seen at 20 mg per day and appeared to plateau at 40 mg per day.

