3.1. Phase 1b (Dose Escalation)

3.1.1. Cohort Size

Cohort size during the Phase 1b portion of the study will be up to 7 patients using a conventional modified 3+3 design for dose escalation studies in oncology. The first cycle (28 days) is defined as the DLT assessment period. At each dose level, 3 or 4 patients will initially be enrolled and followed through the DLT assessment period. If 1 patient in the initial 3 or 4 patients experiences a DLT, the cohort will be expanded to 6 or 7 total patients.

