3.1.1 Phase 1b (Dose Escalation)

During the dose escalation portion of the study, dosing will be based on assigned cohort. Approximately 25 patients are expected to enroll in this phase. Cohort size will be up to 7 patients using a conventional modified 3+3 design for dose escalation studies in oncology.

On Cycle 1 Day 1, in an effort to ensure that patients tolerate oral valganciclovir prior to receiving nanatinostat, valganciclovir will be taken first, followed by nanatinostat approximately 1 hour later. For all subsequent administrations, the sequence of nanatinostat and valganciclovir can be dictated by patient convenience (e.g., both drugs may be taken together if tolerated by the patient). With the implementation of Protocol Amendment 4.0, nanatinostat and valganciclovir will be taken together at all timepoints, including Cycle 1 Day 1.

The first cycle is defined as the dose-limiting toxicity (DLT) assessment period. Grading of DLTs will be according to the National Cancer Institute Common Terminology Criteria for Adverse Events (NCI CTCAE) version 5 and detailed in Section 3.1.5 of the protocol as well as [Section 3.4.1](#) of the SAP. Patients who are unable to complete the DLT assessment period for reasons other than study drug-related toxicity may be replaced if needed to achieve at least 3 patients evaluable for DLTs.

A Safety Review Committee (SRC) comprised of study investigators, the study medical monitor and a Sponsor representative will govern the conduct of the study, and will have the option of defining additional cohorts and doses either below, above, or intermediate to the planned doses as needed based on data generated from prior cohorts. The SRC may also modify the dosing schedule for either nanatinostat or valganciclovir as required to accommodate different dosage strengths and patient convenience. However, when the schedule is adjusted, the total daily dose will remain unchanged. The Phase 1b planned doses for each cohort are provided in Table 2.

Table 2 Phase 1b Dose Levels by Cohort

Cohort Number	Dose Nanatinostat	Dose Valganciclovir
1	10 mg BID (20 mg daily dose)	900 mg BID
2a	5 mg BID (10 mg daily dose)	450 mg BID
2b	10 mg QD (10 mg daily dose)	450 mg BID

Cohort Number	Dose Nanatinostat	Dose Valganciclovir
2c	10 mg QD (10 mg daily dose)	900 mg QD
3	20 mg QD (20 mg daily dose), 4 days on and 3 days off in a 7-day regimen	900 mg QD

BID, twice daily; QD, once daily.

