No formal statistical analysis will be performed to compare cohorts. This study is exploratory in nature; descriptive statistics will be tabulated by study phase and cohort and reviewed to evaluate all study endpoints.

4.1.2 *Summarization by Visit*

In general, data summarized by study visit will be based on the nominal, scheduled visit label as reported on the eCRF. Data collected for the last patient visit will be summarized separately and this summary will be labeled as “End of Treatment” in the analysis.

For laboratory data summaries, data summarized by study visit will be based on the nominal, scheduled visit label as reported on the eCRF when available. If the scheduled visit is not available, then all data collection, including unscheduled and early

termination visits, will be reassigned a study visit based on the actual days relative to baseline using the visit windows identified in [Table 3](#) below.

Table 3 Visit Windows for Analysis

Scheduled Visit	Target Study Day	Study Day Interval
Baseline	0	≤ 0
Cycle 1 Day 1	1	1
Cycle 1 Day 2*	2	2
Cycle 1 Day 8	8	3 – 11
Cycle 1 Day 15	15	12 – 18
Cycle 1 Day 22	22	19 – XX^{**}
Cycle 2 Day 1	$XX + 1$	$XX + 1$
Cycle 2 Day 8	$XX + 8$	$(XX + 2) – (XX + 11)$
<hr/>		
...		

*Note Cycle 1 is the only cycle with a schedule Day 2 visit

** Day 22 is the last scheduled visit within each cycle, and the end of the study interval (XX) is calculated as the day before the start of the subsequent cycle.

If more than one value is mapped to the same visit, the value collected closest to the target study day will be considered for summarization. If two values collected on different days are mapped to the same scheduled visit and are equidistant from the target study day, the earlier of the values will be considered. The visit displayed on subject data listings will be reflective of the scheduled visit label as reported on the eCRF. Study days relative to baseline will be displayed for each visit to indicate to which visit the assessment may have been reassigned, if any.

Otherwise, data collected at unscheduled visits will not be included in by-visit summaries but will be considered when endpoint derivations potentially include multiple visits (e.g., determination of baseline value, determination of worst post-baseline value, etc.). All data will be included in patient listings.

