4.7.2 Plasma Concentrations

The PK sampling schedule with the allowable time window for all patients is displayed in Table 14 in all versions of study protocol. Serial blood samples for the determination of nanatinostat and ganciclovir will be collected on Cycle 1 Day 1 for all patients, and Cycle 2 Day 1 for some patients in Phase 2 capsule cohort and all patients in Phase 2 tablet cohort.

PK collections that have an actual sampling time that is out of time window and deviates by more than 20% of the nominal sampling time will be flagged in the data listings and excluded from the calculation of concentration summary statistics. If an actual blood collection time or a dosing time is missing, the nominal time may be used. Individual plasma concentrations will be presented in data listings and summarized separately using descriptive statistics (number of subjects (N), number of observations (n), arithmetic mean, SD, CV%, median, minimum, and maximum) by nominal time point for each treatment.

Individual plasma concentrations will be plotted by actual time on both linear and semi logarithmic scales. Mean plasma concentrations will be plotted by treatment and nominal time on both linear and semi-logarithmic scales with all treatments overlaid on the same plots.

Plasma PK concentrations will be reported to 3 significant figures in summary statistics except n (and N), and CV%, which will be reported to integer and 1 decimal place, respectively.

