4.9 Changes in the Conduct of the Study or Planned Analyses

The following changes to planned analyses identified within the development of this SAP, relative to the descriptions provided within the clinical study protocol are listed below:

- Section 3.1.3 of the protocol includes a table for intended Phase 1b Cohort Doses.
 - The original intended Valganciclovir dose for Cohort 1 was 900 mg BID, but this was modified per the SRC recommendation after the first

4 patients. The actual Valganciclovir dosing was 900 mg BID for the first 4 patients and then 450 mg BID for the last 3 patients.

- The original intended Nanatinostat dose for Cohort 3 was 20 mg QD. The SRC later recommended to revise this dose to 20 mg QD 4 days per week following review of Cohort 1 safety data.
- Section 3.8 of the protocol states that a central review of patient scans will be performed and may include an assessment based on both Lugano and RECIL criteria. This central review was not performed.
- Section 6.4.1 of the protocol describes urine PK sample collection and, but this was not collected and will not be analyzed.

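### SAP 4.7.4 concludes linear pharmacokinetics whenever the 90% CI for the dose slope includes 1.0, which treats failure to detect a departure as evidence that there is none

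*SAP*

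**What the plan says.** SAP 4.7.4 regresses log(parameter) on log(dose) for nanatinostat Cmax, AUC0-∞ and AUC0-6h, where appropriate. Dose proportionality "will be assessed using the following model using all dose groups". The slope b is tabulated with its standard error and 90% CI, and then comes the decision rule: "If the 90% CI for b includes 1.0, then linearity will be concluded".

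The data behind the fit are described in SAP 4.7.2: "Serial blood samples for the determination of nanatinostat and ganciclovir will be collected on Cycle 1 Day 1 for all patients". Elsewhere the SAP takes a descriptive stance. Section 4.1.1 says: "This study is exploratory in nature; descriptive statistics will be tabulated by study phase and cohort and reviewed to evaluate all study endpoints". Section 4.6.5.5 says that no hypothesis testing is planned, in the context of efficacy. Protocol 12.4.1 plans descriptive and graphical PK evaluation, with modelling if the data suffice, and gives no rule for b.

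**The concern.** Under this rule linearity is the default conclusion, and only a sufficiently precise estimate away from 1.0 can overturn it. That reverses the burden of proof for a positive claim. The fitted model assumes equal variance at all doses. Under that assumption, for any true b other than 1, fewer profiles or noisier profiles make the linear conclusion more likely.

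The information at the low end of the dose range is thin. Only cohort 2a takes 5 mg per administration, and by the cohort rules it has between 3 and 7 patients. PK at varying doses is a secondary objective in both documents. The study report could therefore state that PK is linear when the data show only that no departure was detected.

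**Working it through.** The documents give no power, margin or sample size for this analysis, so there is no stated figure to reproduce. The check is the probability that the rule concludes linearity for a given true b.

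**Inputs**

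- Dose per administration (SAP Table 2): 5 mg in cohort 2a; 10 mg in cohorts 1, 2b and 2c; 20 mg in cohort 3, Phase 2 and the tablet cohort. That this is the regressor is an assumption; the SAP says only dose.
- Phase 1b numbers: "Approximately 25 patients are expected to enroll in this phase. Cohort size will be up to 7 patients". The minimum comes from Protocol 3.1.1: "At each dose level, 3 or 4 patients will initially be enrolled".
- Cohort 1 had 4 + 3 = 7 patients (SAP 4.9): "The actual Valganciclovir dosing was 900 mg BID for the first 4 patients and then 450 mg BID for the last 3 patients". The other four cohorts share 25 − 7 = 18, with 3 to 7 each.
- Add 30 + 10 = 40 patients at 20 mg, for 65 profiles. This allows 22 splits, from 3/15/47 to 7/15/43 at 5/10/20 mg. The actual split is not in the documents.
- Variability from "Table 4: PK Parameters of VRx-3996": Cmax CVs of 121%, 91% and 68% at 5, 10 and 20 mg (3, 4 and 3 patients). For a common CV, the range used is 57% (AUC0-∞ at 10 mg) to 121%.

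**Formulas** (log-normal exposure)

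- σ = √ln(1 + CV²)
- SE(b) = σ/√Sxx, with Sxx taken on ln(dose)
- half-width = t(0.95; 63) × SE, with t = 1.669
- P(conclude linear) = P(|T| < 1.669), where T is noncentral t with 63 df and noncentrality (b − 1)/SE
- exposure relative to proportional over 5–20 mg = 4^(b−1): 0.66 at b = 0.7, 0.50 at b = 0.5, 0.25 at b = 0

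**Example.** For 3/15/47, Sxx = (ln 2)² × (203 − 109²/65) = 9.71. At CV 121%, σ = 0.950, SE = 0.950/√9.71 = 0.305 and half-width = 0.51. At b = 0.5 the noncentrality is −0.5/0.305 = −1.64, and P = 51%.

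**Results.** Common-CV rows use the formula. Dose-specific rows are simulations of the ordinary least-squares fit.

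| Split 5/10/20 mg | CV | Half-width | b = 1 | b = 0.7 | b = 0.5 | b = 0 |
|---|---|---|---|---|---|---|
| 3/15/47 | 57% throughout | 0.28 | 90% | 46% | 10% | 0% |
| 3/15/47 | 121% throughout | 0.51 | 90% | 74% | 51% | 5.5% |
| 7/15/43 | 57% throughout | 0.23 | 90% | 32% | 3% | 0% |
| 7/15/43 | 121% throughout | 0.42 | 90% | 67% | 37% | 1% |
| 3/15/47 | 121/91/68% | 0.36 | 82% | 58% | 30% | 0.8% |
| 7/15/43 | 121/91/68% | 0.30 | 83% | 50% | 19% | 0.1% |

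Results for b = 1.3, 1.5 and 2 mirror those for 0.7, 0.5 and 0. Having 3 rather than 7 patients at 5 mg raises the false linear rate at b = 0.5 from 19% to 30% with dose-specific CVs.

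**Unequal variances.** For 3/15/47, start from a CV of 68% at every dose and raise the 5 and 10 mg CVs to 121% and 91%. At b = 0.9 the linear rate falls from about 86% to about 79%. The reason is that ordinary least squares then understates the SE. At b = 1 the CI covers 1.0 in only 81–84% of runs over the 22 splits, instead of 90%.

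**Sensitivity.** With total daily dose as regressor (10 versus 20 mg, 11/54 to 15/50, common CV 57–121%), linearity is concluded 29–71% of the time at b = 0.5, which is a 1.4-fold departure over that range. With Phase 1b alone (25 patients, assumed 5/15/5), the figure at b = 0.5 is 36% at CV 57% and 51% at CV 74%.

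**The case against.** The strongest reply is that little depends on this. The study is labelled exploratory; b, its SE and its CI are tabulated beside any verdict; geometric means by treatment are reported under SAP 4.7.3; and the analysis is done only where appropriate. No dose or efficacy decision in the documents uses the result. This stands, and it is why severity is low. It does not remove the rule, which sits under a heading for inferential statistics and prescribes a yes-or-no conclusion. If PK is meant to be descriptive, that is a reason to delete the sentence.

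Three stronger readings are tempting and are not supported.

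- A reader might infer that noise always favours the linear conclusion when b is not 1. This holds with equal variances. With unequal variances it can reverse for b near 1, as shown at b = 0.9.
- A reader might take Table 4's low-dose Cmax means as a sign of less-than-proportional exposure. They rest on 3 + 4 + 3 = 10 patients. With Table 4's CVs, the SE of a slope through these doses is about 0.47, so they separate neither b = 1 nor b = 0.5. Over the wider range tested, Protocol 1.8 describes AUC as roughly proportional to dose.
- A reader might treat the percentages as this trial's error rate. The split by dose and the regressor are assumed, and the CVs come from a few patients in a different population. The figures illustrate the rule's behaviour.

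**Conclusion.** The point holds. The rule turns non-rejection of b = 1 into a positive conclusion, and nothing elsewhere in either document limits it. Under the stated assumptions, moderate departures would often be labelled linear: 50–58% of the time at b = 0.7 and 19–30% at b = 0.5 with dose-specific Cmax CVs, and 3–51% at b = 0.5 with a common CV of 57–121%. A four-fold departure over 5–20 mg would rarely be missed: under 1% with dose-specific CVs and at most about 6% with a common CV.

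Sixty-five usable profiles may be optimistic. SAP 4.7.1 excludes Cycle 1 Day 1 profiles with a pre-dose value above 5% of Cmax. In Table 4, AUC0-∞ could not be reliably estimated at 5 mg and had one reliable observation at 20 mg.

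The logical error is certain, while its size is conditional on these assumptions. The consequence is confined to how a secondary PK result is worded.

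**What to change.** Delete the decision sentence in SAP 4.7.4. State instead that b and its 90% CI will be reported, and that an interval containing 1.0 does not by itself establish dose proportionality.

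If a verdict is wanted, set a range for b in advance, conclude proportionality only when the whole 90% CI lies inside it, and otherwise report the result as inconclusive. The range has to match the dose definition used, because the exposure ratio that a given b implies depends on the dose ratio.

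The cost is one or two sentences and no new data. The downside is that a claim of linear PK becomes harder to make, by an amount that depends on the range and the variability. For illustration only, with limits that are assumptions: an exposure ratio of 0.50–2.00 over 5–20 mg corresponds to b from 0.50 to 1.50, since 1 ± ln 2/ln 4 = 1 ± 0.50. With 65 profiles split 5/15/45 and a truly linear drug, the claim would succeed 89% of the time at CV 57%, 67% at CV 74% and 6% at CV 138%. At a true b of 0.5 it would be made wrongly about 5% of the time at most.
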